4.8.3. Follow-up and Outcome Ascertainment Periods

The primary outcome will be ascertained by recording the time of admission and delivery listed in the electronic medical record. The total length of time will be computed in minutes. Follow-up will occur during the postpartum period prior to maternal discharge. Neonatal information will be collected from the neonate's electronic medical record.

5. Statistical Considerations

5.1 Sample Size for Primary Outcome

Assuming an alpha of 0.05 with an 80% power and a standard deviation of 24 hours, 64 patients will be needed in each group to detect a 12 hour difference in means between the groups.

5.2. Power for Other Outcomes

We will have limited power to detect small differences in groups for the secondary outcomes with the exception of patient satisfaction. The surveys being used require limited sample sizes to detect a difference, and 64 patients in each group will adequately satisfy these requirements.

5.3. Analysis Plan

Standard baseline characteristics between the two groups will be collected at baseline. It is assumed that randomization will evenly distribute baseline characteristic differences between the two groups, and thus, we do not anticipate adjusting for these in the primary analysis. Secondary analyses will, though, be analyzed using regression adjustments to account for any possible confounding covariates between the two groups. The primary analysis will be done in an intent-to-treat basis.

The primary analysis will compare the total admission to delivery time in minutes between the two groups. This will be analyzed using a two-sided student's t-test.

5.4. Secondary Aims:

The secondary analyses will be to compare the incidence of certain events between the two groups. A Chi-square p-value, relative risk, and 95% confidence interval will be calculated.

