Induction of labor is necessary in one-fourth of women and a large proportion require cervical ripening. Cervical ripening is necessary to shorten the time to delivery and increases the chances of a vaginal delivery. The superior method for cervical ripening has long been debated. The two techniques utilized are mechanical and pharmacological methods. Pharmacological techniques center on formulations of prostaglandin but are associated with higher risks of tachysystole compared to mechanical methods. The primary mechanical method used is a transcervical Foley catheter with the balloon filled with 30-80 mL of sterile fluid. Downward tension on the internal os by the filled balloon leads to production of endogenous prostaglandins leading to remodeling of the cervix. A Cochrane review has shown similar efficacy between pharmacological and mechanical methods, but both were found to be superior to oxytocin for cervical ripening.

There has only been one randomized controlled study evaluating the transcervical Foley catheter for cervical ripening in the outpatient setting. The primary outcome of this study was a change in the Bishop score between the groups, and it found the Bishop scores were similar between the two groups. While not powered to detect a difference, it did show women in the outpatient group spent less time in the hospital without any adverse events. Outpatient cervical ripening is an attractive alternative to women and physicians because of the decreased amount of time spent in the hospital and opportunity for patients to be in the comforts of their home; however, few have adopted this method since there is only one study evaluating outpatient cervical ripening with a transcervical Foley catheter. The safety of the transcervical Foley catheter has been well-established, though, and it is not associated with increased risks of adverse events such as chorioamnionitis, endometritis, placental abruption, or stillbirth.

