In our institution, cervical ripening is exclusively performed using a transcervical 16 French Foley catheter with 30mL of sterile saline. This method has been proven to shorten the time to delivery compared to the PGE2 vaginal insert without increasing the cesarean delivery rate [Edwards 2014]. Additionally, Pettker et al [Pettker 2008] demonstrated there was not benefit to adding oxytocin to the transcervical Foley catheter induction method. Patients requiring cervical ripening spend a considerable amount of time in the latent phase. This prolonged period of time represents a significant portion of patients' intrapartum hospital costs. Additionally, while patients are not confined to bed, many patients choose to immobilize themselves during this period. As such, our objective is to evaluate the feasibility, safety, patient satisfaction, and cost associated with outpatient as compared to inpatient induction of labor with Foley catheterization for cervical ripening in low-risk women in a single academic institution in the southern United States. Contrary to Sciscione et al's [Sciscione 2001] study where the primary outcome was change in Bishop score, our study will be powered to detect a 12 hour reduction in time from admission to delivery.

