3.4 Study Population and Eligibility Criteria

a. Inclusion criteria:

- i. Age ≥ 18
- ii. Multiparous
- iii. Singleton gestation
- iv. Gestational age between 39+0 and 42+0 weeks.
- v. Vertex presentation
- vi. Cervix ≤ 3 cm. If cervix is between 2 and 3 cm dilated, it must be $<80\%$ effaced
- vii. No prior cesarean section or uterine surgery
- viii. Resides within Jefferson County
- ix. Access to a telephone
- x. Reliable transportation

b. Exclusion criteria:

- i. Unsuitable for outpatient Foley placement management (IUGR, oligohydramnios, prior cesarean delivery, gestational hypertension, preeclampsia, uncontrolled chronic hypertension, complex maternal disease, provider discretion). Women with pregestational diabetes and those with gestational diabetes requiring medication will be excluded.
- ii. Latex allergy
- iii. Contraindication to induction of labor
- iv. Evidence of labor
- v. Fetal anomaly or demise
- vi. Inability to give consent (non-English, inability to read or write)

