3.6 Study groups

There will be two intervention groups:

a. All patients:

- a. Patients will present to the 2nd floor of the CRWH for a scheduled OFFSITE study visit. This will occur every weekday except Friday.
- b. The order of events in the CRWH for all patients will be as follows:
 - i. Blood pressure evaluation
 - ii. Transabdominal ultrasound
 - iii. Vaginal examination
 - iv. Continuous fetal heart rate and tocometry monitoring for 20 minutes.
- c. If the patient's blood pressure is normal (<140 mmHg systolic and < 90 mmHg diastolic), ultrasound identifies a vertex fetus with normal amniotic fluid, cervix meets inclusion criteria (< 3 cm. If between 2-3 cm, then < 80% effaced), and the fetal heart rate tracing is category 1* without evidence of three contractions in a ten minute period, then the patient will be consented and randomized to either group 1 (standard treatment) or group 2 (intervention) and management will follow as detailed below.
 - i. Patients who do not meet cervical dilation criteria because of not needing cervical ripening (cervix >3 cm, or if 2-3 cm dilated and > 80%) will have their induction of labor canceled unless they are patients of the PrimeCare division.

b. Group 1 (Standard treatment)

- a. The patient will return the next day for her scheduled induction of labor at a pre-assigned time.
- b. Patient will be admitted to the labor and delivery floor and will be registered in the standard fashion by the nurse. The physician will be notified when the patient has had a reassuring fetal heart rate tracing and is ready for placement of the Foley catheter.
- c. The physician will perform an ultrasound to confirm vertex position and check the cervix. The patient will remain in the study even if she no longer meets cervical exam requirements (≤ 3 cm, if 2 cm, < 80% effaced) since the study design is intent to treat.

- d. Using the standard technique (dorsal lithotomy, betadine prep, sterile ring forceps, balloon inflated to 30 ml sterile saline), the transcervical Foley catheter will be placed transcervically. It is at the provider's discretion to tape this to the inner thigh or to leave it un-taped.
 - i. If the transcervical catheter is unable to be placed with a speculum and ring forceps, the provider may place with digital guidance.

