4.2 Randomization

Randomization will occur after eligibility/exclusion criteria are confirmed and informed consent is obtained. Randomization will occur by a predetermined computer-generated block randomization scheme prepared by a study statistician. A variable block design will be utilized.

Women randomized to the standard inpatient (control) group will be scheduled for cervical ripening in the UAB Women and Infants Center. The patients randomized to the outpatient (intervention) group will undergo placement of the transcervical Foley catheter per the protocol, and a scheduled time to report to the UAB Women and Infants Center the following morning for their induction of labor will be given to the patient.

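### Cheap improvement, not an error: the unadjusted primary t-test is sound, but prespecifying study-visit cervical dilation as one covariate might add a little precision at a cost of at most about 0.3 power points

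*Combined protocol and SAP*

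**What the plan says.** **Analysis.** Section 5.3 makes the primary analysis an intent-to-treat, two-sided Student's t-test of admission-to-delivery minutes. It assumes that randomization will balance baseline characteristics and says "we do not anticipate adjusting for these in the primary analysis". The next sentence keeps regression adjustment for secondary analyses. It names no covariates and does not say whether the primary outcome is among the outcomes adjusted.

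**Size.** Section 5.1 assumes alpha 0.05, 80% power and an SD of 24 hours, and concludes that "64 patients will be needed in each group to detect a 12 hour difference in means between the groups".

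**The examination.** Section 3.6, under all patients, begins its list with "The order of events in the CRWH for all patients will be as follows" and puts a vaginal examination third, before fetal monitoring. The cervical finding helps decide eligibility, and consent and randomization follow. Section 4.2 agrees on the order: "Randomization will occur after eligibility/exclusion criteria are confirmed and informed consent is obtained". It specifies variable blocks and no stratification factor.

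**Later examinations.** In Group 1 the cervix is examined again at admission the next day: "The physician will perform an ultrasound to confirm vertex position and check the cervix". Under section 4.3, a failed catheter placement in either group leads to a further attempt 24 to 72 hours later.

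**The concern.** Expected balance is a reason not to worry about confounding. It is not a reason to ignore precision: a prognostic covariate removes outcome variance from the treatment comparison even when the arms are perfectly balanced. Section 5.3 does not consider this.

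Cervical dilation is a natural candidate because the trial already obtains it. The protocol also links the state of the cervix to time. The opening summary says "Cervical ripening is necessary to shorten the time to delivery and increases the chances of a vaginal delivery", and section 2.1 says "Patients requiring cervical ripening spend a considerable amount of time in the latent phase". If dilation is prognostic among eligible women, the same 128 women would give a somewhat narrower confidence interval for the primary outcome.

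The choice of examination matters. The Group 1 check at admission comes after randomization, so it is not a valid baseline value. A covariate described only as baseline cervix could mix the two.

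**Working it through.** **Inputs.** From 5.1: difference 12 h, SD 24 h, alpha 0.05, 64 per group. From 5.3: two-sided t-test. The R2 of dilation for the outcome is not in the documents. It is an assumption and is shown over a range.

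**1. The plan's own figure.** The standardized difference is 12/24 = 0.5. The noncentrality is 0.5 × sqrt(64/2) = 2.828 on 126 df, which gives 80.1% power. The exact t calculation needs 63.77 per group, rounded up to 64. Section 5.1 reproduces.

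**2. One covariate, equally predictive in both arms.** The model has 125 df. Its noncentrality is 2.828 × sqrt((1 - b)/(1 - R2)), where b is the squared chance correlation between arm and covariate. Under randomization b follows Beta(1/2, 63), with mean about 0.008, and power is averaged over it. The last column is the size at which an unadjusted t-test would have the same power.

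| Assumed R2 | Power | Change from 80.1% | Mean 95% CI half-width | Equivalent t-test size per group |
|---|---|---|---|---|
| 0 | 79.8% | -0.3 | 8.41 h | 63.5 |
| 0.04 | 81.4% | +1.3 | 8.24 h | 66.1 |
| 0.10 | 83.8% | +3.7 | 7.98 h | 70.4 |
| 0.20 | 87.8% | +7.7 | 7.52 h | 79.1 |

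The unadjusted mean half-width is 8.38 h. Break-even is at R2 of about 0.008. Simulation (200,000 trials per setting) agrees with these powers within 0.2 points. If chance imbalance is ignored, the loss at R2 = 0 is below 0.1 point, so 0.3 is the less favourable figure.

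**3. Predictive in the inpatient arm only.** The outpatient arm ripens at home before the admission clock starts, so this case deserves equal attention. With slope β in one arm and none in the other, the common slope is β/2. It removes about a quarter of the inpatient-arm R2 from the average residual variance: R2 = 0.10 acts like 0.025, and 0.30 like 0.075. The formula in step 2 then gives 80.8% and 82.8%. Simulation (400,000 trials per setting) gives 80.9% at 0.10, 81.9% at 0.20 and 82.9% at 0.30. The gains over the t-test on the same simulated data are 0.7, 1.6 and 2.7 points. Break-even lies between R2 = 0.02 (-0.1 point) and 0.04 (+0.1 point).

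**4. Validity of the adjusted model.** With no mean difference and inpatient-only R2 of 0.10, 0.20 or 0.30, type I error was 5.0% each time (200,000 trials each). Drawing dilation in 0.5 cm steps from 0 to 3 cm, in place of a normal covariate, changed results by at most 0.4 points.

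**The case against.** **The plan's choice is legitimate.** It is explicit, unbiased and matched to the sample size. This stands in full. A reader might infer that leaving out adjustment biases the comparison or leaves it short of power. Step 1 shows that it does not.

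**Adjustment is already planned.** Section 5.3 provides it for secondary analyses. This stands in part: no covariate is named, so the present proposal names one and changes which analysis is primary.

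**No benefit is documented.** This also stands. The opening summary describes what ripening does, and section 2.1 describes women who need it. Neither measures a gradient among eligible women. Section 3.4 caps dilation at 3 cm and narrows the range further: "If cervix is between 2 and 3 cm dilated, it must be" less than 80% effaced. Next-day re-examination and repeat placement attempts may weaken the link too. A reader might infer that a gain of up to about 4 points is realistic. The documents do not support that: +3.7 needs R2 = 0.10 in both arms, and the low end is slightly negative.

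**The timing is not fully settled.** Section 3.6 puts consent and randomization after the examination, but 4.1 has consent signed at a clinic appointment in weeks 37 to 42. The first footnote of 3.6 counts a woman without a category 1 tracing before placement in the outpatient group, although the same section makes that tracing a condition of randomization. This stands, and it adds a step to the fix.

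**Dilation is not the only candidate.** Eligibility also uses effacement. Dilation alone is proposed because it keeps the cost to one degree of freedom; the documents do not show it to be the better predictor.

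**Conclusion.** This is an optional, low-cost improvement. The unadjusted t-test is sound, and its 80.1% power holds for a single final test with 64 women analysed per group. That limit matters: 5.5 plans an interim analysis with no stated alpha allocation, 5.1 states no allowance for losses, and 4.4 lets some women withdraw. For example, with 61 or 58 analysed per group (assumed losses), power would be about 78.2% or 76.1%. Covariate adjustment does not resolve the interim question, which is separate.

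The size of the benefit is unknown. It runs from about -0.3 points if dilation is not prognostic to +3.7 at R2 = 0.10 in both arms, and stays under +3 even at R2 = 0.30 if dilation predicts only among inpatients. The case for the change is that the loss is small and bounded while a gain is possible. It rests on the SD and difference in 5.1, a linear effect of dilation, and an examination that does precede randomization.

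**What to change.** Before any comparative data are seen, amend 5.3 as follows:

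- Make the primary analysis a linear model of admission-to-delivery minutes on randomized group plus one covariate: cervical dilation in cm, as a linear term, from the study-visit examination in 3.6.
- State that the Group 1 check at admission and any repeat examination after a failed placement are not used.
- Record the study-visit value for every woman.
- Keep the unadjusted t-test as the supporting analysis.

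Also state that this examination precedes randomization. Reconcile the order of consent, examination, tracing and randomization across 3.6 (including its first footnote), 4.1 and 4.2.

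The cost is the added wording, one recorded value from an examination already scheduled, one degree of freedom (126 to 125), and at most about 0.3 power points. No extra patients or visits are needed.

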5.5. Interim Monitoring

We propose an interim analysis when 32 patients in each group have completed the study (50% completion) to determine whether continuation of the study is necessary. We do not propose a formal stopping rule for safety, but the DSMB will continually monitor the study for safety.

6. Future studies

If our results show outpatient transcervical Foley catheter placement is safe, well-tolerated, and reduces hospital admission time to delivery, we will submit a Patient Centered Outcomes Research Institute (PCORI) grant to conduct a multi-center trial in an attempt to alter current induction methods and ultimately improve patient satisfaction and outcomes.

7. References

- 1) World Health Organization: WHO recommendations for induction of labour, Department of reproductive health and research. Geneva, Switzerland: World Health Organization; 2011:32.
- 3) Wing DA. Labor induction with misoprostol. *Am J Obstet Gynecol* 1999 Aug;181(2):339-45.

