4.7 Adverse Event Reporting

A Data Safety Monitoring Board (DSMB) will be formed and consist of three individuals within the Division of Maternal-Fetal Medicine and Department of Pediatrics who have no ties to the study design, evaluation of results or potential authorship of the manuscript. The primary purpose of the DSMB will be to monitor patient safety. The members of this board are Drs. [name] (obstetrician), [name] (epidemiologist), and [name] (pediatrician).

The purpose of the study is to determine whether outpatient cervical ripening shortens the admission to delivery timing compared to the standard inpatient method. The safety of a transcervical Foley catheter has already been established, and it does not increase the risk of adverse events such as chorioamnionitis, placental abruption, non-reassuring fetal heart rate tracings, cesarean section, or stillbirth.

We define an adverse event as an undesirable experience or outcome occurring in a research participant, regardless of whether participation in the research study caused the event to occur. For example, placental abruption and/or stillbirth are known risks of pregnancy, and while not known to be related to transcervical Foley catheter usage, would be considered an adverse event if it occurred during the study. All serious adverse events will be reported to the DSMB and IRB. A serious adverse event will include the following events.

- a. Death
 - a. Maternal
 - b. Fetal (stillbirth)

- b. Life-threatening
- c. Prolonged hospitalization
- d. Disability or permanent damage
- e. Intervention required in an attempt to prevent permanent impairment or damage (i.e. non-reassuring fetal heart rate tracing while the transcervical Foley catheter is in place necessitating an emergent delivery.
- f. Other serious or important medical events:
 - a. Placental abruption
 - b. Chorioamnionitis diagnosed while the transcervical Foley catheter remains in place
 - c. Any other serious event necessitating a higher level of care, such as a transfer to an intensive-care unit.
- g. Any other event not listed that the investigators believe may have been caused by the intervention.

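### The interim look at 32 per group can end the trial but has no stated outcome, boundary or adjusted final level, so the 5% type I error is not secured

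*Combined protocol and SAP*

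**What the plan says.** - Section 5.5 plans "an interim analysis when 32 patients in each group have completed the study (50% completion) to determine whether continuation of the study is necessary". The sentence after it turns to safety: "We do not propose a formal stopping rule for safety", with the DSMB watching safety throughout.
- Section 5.1 gives the only error rate in the plan: "Assuming an alpha of 0.05 with an 80% power and a standard deviation of 24 hours", leading to 64 patients per group for a 12-hour difference in means.
- Section 5.3 says of the primary comparison: "This will be analyzed using a two-sided student's t-test". No significance level is attached.
- Section 4.7 sets up the DSMB and states: "The primary purpose of the DSMB will be to monitor patient safety". It gives no efficacy or futility boundary and does not assign the interim decision to the board.

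No section names the interim outcome, the direction of stopping, a threshold, or an adjusted final level. Section 5.5 shows no sign of redacted text.

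**The concern.** An analysis whose purpose is to decide whether the trial goes on is a chance to stop. If it can stop for benefit, it is a second chance to declare success, and two chances at 5% give more than 5% overall unless the levels are set jointly.

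Because 5.5 treats safety separately and 4.7 gives the DSMB a mainly safety role, the look reads most naturally as one at the primary outcome. The text does not settle that, and it does not say whether benefit or futility is meant. The rule could therefore be chosen after half the data are available, and a reader of the final p-value could not tell which error rate applies. An early stop on a loose threshold would also tend to overstate the hours saved. Section 6 makes a favourable result the basis for a multi-centre grant application, so an overstatement would carry forward.

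**Working it through.** **Inputs.** Section 5.1: alpha 0.05, power 80%, SD 24 h, difference 12 h, 64 per group. Section 5.3: two-sided t-test. Section 5.5: one look at 32 per group, so the information fraction is 32/64 = 0.5.

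**1. The plan's own sample size.** The normal formula gives n = 2 × 24² × (1.960 + 0.842)² / 12² = 62.8, or 63 per group. The exact noncentral-t power is 79.5% at 63 and 80.1% at 64. The stated 64 is thus reproduced as a single-look, two-sided t-test, with no allowance for a second look.

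**2. Type I error if the look may stop for benefit.** Under the null, the interim and final statistics Z1 and Z2 are bivariate normal with correlation √0.5 = 0.707. With interim cut-off c and the final test at two-sided 0.05, the overall error is P(|Z1| > c or |Z2| > 1.96).

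| Interim two-sided threshold | c | Overall type I error |
|---|---|---|
| p<0.001 | 3.291 | 0.0502 |
| p<0.005 | 2.807 | 0.0519 |
| p<0.01 | 2.576 | 0.0546 |
| p<0.025 | 2.241 | 0.0643 |
| p<0.05 | 1.960 | 0.0831 |

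Simulated t-tests at 32 and 64 per group (300,000 trials) give 0.0833 for the last row.

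**3. If the look may stop only for futility.** The error does not rise. As an illustration, stopping when interim p>0.5 gives a type I error of about 0.046 and power of 77.5%, against 80.1% without the look.

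**4. Boundaries that restore 5%.**
- O'Brien-Fleming: setting c1 = √2 × c2 and solving for overall 0.05 gives z = 2.797 and 1.977, that is p = 0.0052 at the interim and 0.0480 at the end.
- Haybittle-Peto: interim p<0.001 with the final test at 0.05 gives 0.0502. Exact control needs a final level of 0.0498.

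**5. Behaviour when the true difference is 12 h.** At 32 per group the standard error is 24 × √(2/32) = 6 h and the 5% critical t value is 2.00. An unadjusted stop therefore needs an observed difference of about 12 h or more, which happens in about half of trials. Simulation gives:

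| Rule | Stops early | Mean estimate if stopped | Mean over all trials |
|---|---|---|---|
| Unadjusted, p<0.05 | 50% | 16.7 h | 13.2 h |
| O'Brien-Fleming | 20% | 20.2 h | 12.8 h |
| Haybittle-Peto | 8% | 22.5 h | 12.4 h |

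Simulated power at 64 per group is 79.9% with O'Brien-Fleming and 80.2% with Haybittle-Peto.

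**The case against.** The strongest reply is that the harm is conditional. Section 5.5 never says that the look tests the primary outcome or may stop for benefit, and its wording also fits futility. Reaching 0.083 takes three assumptions: the primary outcome is tested, stopping for benefit is allowed, and the interim threshold is 0.05. That 0.05 is stated in 5.1 for the sample size, not for the interim. With a strict threshold of p<0.005 or lower the excess is at most about 0.002. All of this stands, and 0.083 is an illustration rather than a prediction. It is not an upper bound either: an interim threshold of 0.10 would give 0.125 by the same formula.

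Three smaller points also stand. Haybittle-Peto with a final 0.05 is itself at 0.0502, so strict control needs 0.0498. O'Brien-Fleming at 64 per group falls a fraction below the planned 80% power. A boundary only modestly reduces the average overstatement, from 13.2 h to 12.8 h or 12.4 h.

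The plan does name a monitoring board independent of the study design, so oversight is not absent. The board is not given the interim decision, however, and it has no rule to apply.

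None of this supplies the missing rule. The plan does not limit the look to futility and does not commit to a strict threshold.

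**Conclusion.** The concern holds, and the plan must be corrected. As written, the look can end the trial under a rule that is nowhere stated, so the 5% error rate in 5.1 cannot be established from the plan.

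The size depends on what is left open. If the look tests the primary outcome, may stop for benefit at a threshold between 0.001 and 0.05, and the final test stays at 0.05, the overall error is 0.050 to 0.083. If it is for futility only, there is no inflation, but power may be lost. The omission itself is certain; how much inflation would follow is not. The 64 per group is correct for a single look.

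**What to change.** In 5.5, state that the look concerns admission-to-delivery time, who carries it out, who decides, and whether stopping for benefit is allowed. Then choose one of the following.

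- **Stopping for benefit allowed.** Stop at 32 per group only if two-sided p<0.0052, and test at p<0.0480 in the final analysis in 5.3 (O'Brien-Fleming). Alternatively, use interim p<0.001 with the final test at 0.05 (Haybittle-Peto, overall 0.0502), or at 0.0498 for exact control. State in 5.1 that alpha 0.05 covers two looks, adding that this is approximate if the final level stays at 0.05 under Haybittle-Peto.
- **Stopping for benefit not allowed.** Say so, and keep the final test at 0.05.

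In either case, make any futility rule non-binding. The choice between the two boundaries is a matter of preference; fixing one in advance is not. If the trial stops early, report the estimate with a caution, because a boundary makes overstatement rarer but larger when it occurs.

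The cost is a few sentences in 5.1, 5.3 and 5.5. No added recruitment is needed if power of about 79.9% under O'Brien-Fleming is accepted against 80.1% for a single look. Haybittle-Peto costs essentially nothing.
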